10 STUDY POPULATION

10.1 Recruitment

The subjects will be recruited from a list of healthy volunteers at CTC and from advertising in media.

10.2 Screening and enrolment log

A screening number will be allocated to each subject undergoing screening. Investigators must keep a record of all screened subjects even if they were not subsequently included in the study. This information is necessary to verify that subjects were selected without bias. The reason for screening failure should be stated for all subjects screened but not included. The reason for withdrawal should be stated for all subjects included but not completed.

All subjects who have signed the Informed Consent Form (ICF) will be assigned a screening number (S0001, S0002 and S0003 etc.). Subjects included and randomized will be assigned a subject number (101, 102 and 103 etc.).

10.3 Number of subjects

The study will include 18 subjects.

10.4 Inclusion criteria

For inclusion in the study, subjects must fulfill the following criteria:

- Snus user, with a minimum weekly consumption of three or more snus cans (brands with nicotine content <1%) or two or more cans (brands with nicotine content >1%) since ≥1 year.
- 2. Consent to participate voluntarily and sign Informed Consent Form prior to any study procedure.
- 3. Healthy male/female, age ≥ 19 .
- 4. Willing and able to comply with study procedures.

5. A heart rate increase ≥ 10 beats/min with first use of snus in the morning after overnight abstinence from any nicotine exposure.

10.5 Exclusion criteria

Subjects must not enter the study if any of the following exclusion criteria are fulfilled:

- 1. Smoker, defined as "smoking during the last 24 hours according to self-report and CO in exhaled air >10 ppm at clinical visits".
- 2. A history or presence of diagnosed hypertension or any cardiovascular disease.
- 3. Surgery within 6 months of the screening visit that, in the opinion of the investigator, could negatively impact on the subject's participation in the clinical study.
- 4. Any surgical or medical condition, which, in the judgment of the clinical investigator, might interfere with the absorption, distribution, metabolism or excretion of the investigational product.
- 5. History of any clinically significant disease or disorder which, in the opinion of the Investigator, may either put the subject at risk because of participation in the study, or influence the results or the subject's ability to participate in the study.
- 6. Pregnancy or planning to get pregnant during the study.
- 7. Positive screen for drugs of abuse at screening or on admission to the unit prior to administration of the investigational product.
- 8. Any positive result on screening for serum hepatitis B surface antigen, hepatitis C antibody and Human Immunodeficiency Virus (HIV).
- 9. Current or history of alcohol abuse and/or use of anabolic steroids or drugs of abuse.
- 10. Use of any prescribed or non-prescribed medication including antacids, analgesics and herbal remedies within two weeks prior to the first administration of IP, except occasional intake of paracetamol (maximum 2 000 mg/day; and not exceeding 3 000 mg/week), at the discretion of the Investigator.
- 11. Plasma donation within 1 month of Screening or any blood donation/blood loss >450 mL during the 3 months prior to Screening.
- 12. Investigator considers the subject unlikely to comply with study procedures, restrictions and requirements.

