Subjects report to the clinic on separate days for the 5 experimental sessions. The subjects are instructed to abstain from snus or other nicotine delivery products as from the evening before and smoking 24 hours prior to all visits to the clinic. All sessions are performed during the morning hours to facilitate abstinence. The subjects should certify abstinence before each treatment is started.

The treatments are administered as single doses in a pre-determined randomized order. The subject keeps the pouch still between the upper lip and the gum for 60 minutes and are instructed not to manipulate the pouch with the tongue or lips. The subjects are instructed not to eat or drink from 30 minutes before and during application of investigational products and 30 minutes after the investigational product have been taken out. [5].

Each used pouch is collected and frozen $(-20^{\circ}C)$ pending analyses of nicotine. Unused pouches are collected and frozen $(-20^{\circ}C)$ pending analysis and serve as references in the calculations of extracted doses.

Investigational Products, dosage and mode of administration

Test articles:

1= ZYN Smooth containing 3 mg nicotine per portion

2= ZYN Smooth containing 6 mg nicotine per portion

3= ZYN Smooth containing 3 mg nicotine per portion (alternative manufacturing process)

4= ZYN Smooth containing 6 mg nicotine per portion (alternative manufacturing process)

Reference articles:

5= Swedish portion snus PSWL 1.0 g (8 mg nicotine/g)

Duration of treatment

The treatments are administered as single doses in a pre-determined randomized order. The subject keeps the pouch still between the upper lip and the gum for 60 minutes. Plasma concentrations of nicotine are followed over 6 hours.

Duration of subject's involvement in the study

Each Subject will participate in the study approximately 20-84 days.

Efficacy assessments

Pharmacokinetics assessments - WinNonlin computer program (Certara Corp., USA) will be used for pharmacokinetic calculations. Nicotine plasma concentrations are determined at preset time points, before *(0), 5, 10, 15, 30 and 60* minutes, 1.5, 2, 4 and 6 hours after administration.

Pulse rate – Pulse rate will be measured at the following time points: before (0), 5, 10, 15, 30 and 60 minutes after each product is administered.

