9 INVESTIGATIONAL PLAN

9.1 Overall study design and schedule of events

The study will be conducted as an open, randomized, five-way cross-over, single dose administration. The study will include 18 subjects.

The subjects included will be healthy males and females aged ≥ 19 years who use tobaccobased snus, since ≥ 1 year with a weekly consumption of three or more snus cans (brands with nicotine content $\leq 1\%$) or two or more cans (brands with nicotine content $\geq 1\%$). Subjects who are pregnant or who have a history of hypertension or any cardiovascular disease are excluded. Subjects shall be abstinent from snus and all other nicotine containing products from 8.00 p.m. the night before each trial day.

Before entry to the study subjects undergo screening evaluations including smoking and snus use, medical history and pulse rate measurements before/after application of their usual brand of snus. The puls rate assessment will be made in abstinent condition from 8 p.m. the night before.

A pulse rate increase of ≥ 10 beats/min in the morning before use of any nicotine containing product will classify the subject as eligible for participation the study.

Subjects report to the clinic on separate days for the 5 experimental sessions. The subjects are instructed to abstain from snus, cigarettes or other nicotine delivery products as from 8 pm the evening before. All sessions are performed during the morning hours to facilitate abstinence. The subjects should certify abstinence before each treatment is started.

The treatments are administered as single doses in a pre-determined randomized order. The subject keeps the pouch still between the upper lip and the gum for 60 minutes and are instructed not to manipulate the pouch with the tongue or lips. The subjects are instructed not to eat, drink, chew chewing gum or brush teeth from 30 minutes before application of treatment, during application of investigational products and 30 minutes after the investigational product have been taken out. [5].

Each used pouch is collected and frozen (-20°C) pending analyses of nicotine.

Assessment	Screening	Cross-over phase	Follow-up Phone contact
	Visit 1 ¹	Visit 2-6 ²	Visit 7
	Day -14 to -1	Day 1 followed by 1-14 day(s) of wash-out. Repeated for each dose time point	7 Days after last dose – 3/+7 days
Informed consent	Х		
Eligibility	Х	X ⁸	
Demographics	Х		
Prior and Concomitant medication	Х	X	X
Medical history	Х		
Urine pregnancy test ³	Х		

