10.6 Restrictions during the study

- 1. Subjects shall be abstinent from snus and all other nicotine containing products from 8.00 p.m. the night before each trial day.
- 2. Subjects shall abstain from smoking the last 24 before each study day.

- 3. The subjects are not allowed to eat or drink, or use any other mouth related procedure (e.g. tooth brushing) 30 minutes before dose administration, during application of investigational products and 30 minutes after the investigational product have been taken out. [5].
- 4. Other therapy considered necessary for the subject's welfare may be given at the discretion of the Investigator. All such therapy must be recorded in the Case Report Form.
- 5. The female volunteers are expected to be sexually abstinent or use contraceptives to prevent pregnancy during the study period
- 6. Consumption of grapefruit and/or grapefruit containing products is not allowed 1 week before IP dosing until last PK day.
- 7. Xanthine or taurine containing products/beverages, e.g. Redbull, are not allowed during the study.
- 8. Abstain from drugs of abuse from Screening to Follow-up visit.
- 9. The subjects must not donate blood or plasma during the study until three months after the Follow-up Visit.
- 10. Study subjects are not allowed to participate in any other clinical study during the study period.

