12.4.7 CO test

Measurement of Carbonmonoxide in exhaled air will be performed at visits to the clinic.

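### Exclusion 1 needs both admitted smoking and CO above 10 ppm, so a raised CO with a denial triggers no stated action; the smoking-abstinence windows also disagree

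*Protocol*

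**What the plan says.** Three parts of the protocol bear on smoking before a session.

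- **Eligibility.** Section 10.5, exclusion 1, excludes smokers, defined as "smoking during the last 24 hours according to self-report and CO in exhaled air >10 ppm at clinical visits". Table 1 schedules eligibility at screening and, by its footnote 8, in the cross-over phase only before dosing at Visit 2.
- **Abstinence.** The synopsis tells subjects to "abstain from snus or other nicotine delivery products as from the evening before and smoking 24 hours prior to all visits to the clinic". Section 10.6, no. 2, reads "Subjects shall abstain from smoking the last 24 before each study day", with no unit after the number. Section 9.1 puts cigarettes under the same evening cut-off as snus: subjects are to "abstain from snus, cigarettes or other nicotine delivery products as from 8 pm the evening before".
- **Verification.** At each session, "The subjects should certify abstinence before each treatment is started"; no window is attached to what is certified. Section 12.4.7 says "Measurement of Carbonmonoxide in exhaled air will be performed at visits to the clinic", and Table 1 lists CO at screening and Visits 2-6. Neither place gives a limit or an action.

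**The concern.** An exhaled CO test is useful because it does not depend on what the subject says. Under exclusion 1 as worded, a raised CO counts only if the subject has also admitted smoking, so the objective check adds nothing in the one situation where it is needed. The per-session safeguard is also a self-declaration.

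The primary endpoint is AUCinf of plasma nicotine, and pulse rate and VAS ratings serve as proxies for nicotine uptake. Nicotine from a cigarette smoked shortly before a session is measured along with nicotine from the pouch. Comparisons are within subject in 18 subjects, so nicotine carried into one period does not cancel against the subject's other periods.

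The two abstinence windows are a second, smaller matter: staff and subjects cannot tell which rule is being certified.

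**Working it through.** **1. Exclusion 1 as worded.** There are four combinations of self-report (last 24 h) and CO:

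| Self-report | CO | Excluded by no. 1? | Other stated control |
|---|---|---|---|
| Admits | >10 ppm | Yes | 10.6; certification |
| Admits | ≤10 ppm | No | 10.6; certification |
| Denies | >10 ppm | No | None explicit; exclusion 12 by investigator judgement |
| Denies | ≤10 ppm | No | None needed on the stated criteria |

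One of four combinations is excluded. If either condition sufficed, three of four would be. The third row is the real gap.

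**2. Visits 2-6.** The definition refers to clinical visits in the plural, but Table 1 schedules no eligibility check after Visit 2. CO is read at Visits 3-6 without a stated decision attached.

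**3. The windows.** The protocol says only that "All sessions are performed during the morning hours to facilitate abstinence". Assuming dosing between 08:00 and 12:00, abstinence from 8 pm lasts 12 to 16 h, against 24 h elsewhere (reading the missing unit in 10.6 as hours). The gap is 24 − 16 = 8 h to 24 − 12 = 12 h. A subject who smoked at 6 pm the day before complies with Section 9.1 but breaches the synopsis and Section 10.6.

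**4. Effect of the window conflict on AUCinf.** Assume a nicotine half-life of 2 h (not in the protocol).
- Fraction left after 12 h = (1/2)^(12/2) = 1/64, about 1.6%.
- To leave 2 to 5 ng/mL at dosing, the 8 pm level would have to be 64 × 2 = 128 to 64 × 5 = 320 ng/mL, above the 100 ng/mL top of the assay range in Section 12.5.1.

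Snus is in any case permitted until 8 pm under Section 10.6, no. 1.

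**5. Effect of a same-morning cigarette that goes undetected.** Assume residual nicotine C0 of 2 to 5 ng/mL at dosing, the same 2 h half-life, and first-order elimination. None of these values is in the protocol.
- λ = ln 2 / 2 h = 0.347 per h.
- Added AUCinf = C0/λ.
- C0 = 2: 2/0.347 = 5.8 ng·h/mL.
- C0 = 5: 5/0.347 = 14.4 ng·h/mL.

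The addition is proportional to both the assumed residual and the assumed half-life, and applies to one period of one subject. With all 18 subjects contributing, one such period moves the mean within-subject difference by 5.8/18 = 0.3 to 14.4/18 = 0.8 ng·h/mL.

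**The case against.** The best case for the protocol has four parts.

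**Other controls exist.** A reader might infer from exclusion 1 that someone who admits smoking that morning and reads 9 ppm may be dosed. The protocol does not support that: the subject breaches Section 10.6, nos. 1 and 2, and the Section 9.1 instruction, and could not truthfully certify abstinence. Inclusion 4 and exclusion 12 also concern compliance with study procedures and restrictions. This stands for the admitted case, although Section 10.6 does not spell out what happens to the session. For the denied case with raised CO, exclusion 12 leaves the decision to judgement.

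**The wording may have meant assessment by both methods.** That is possible, but the sentence does not say so, and a criterion that can be read two ways still needs correcting.

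**Contamination would be visible.** A pre-dose plasma sample is taken in every period and the assay range starts at 0.5 ng/mL, so 2 to 5 ng/mL would be measured. The statistical analysis plan, not shown here, may say how pre-dose concentrations are handled. This largely stands. Its limits are that the samples are frozen and sent to an outside laboratory, so the result comes after dosing, and nicotine alone does not identify its source.

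**Sporadic smoking does not favour a product.** Treatment order is randomized, and nothing in the protocol suggests that smoking would cluster on one product. This stands: the expected effect is mainly extra variability.

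**Conclusion.** The concern holds in a limited form. Exclusion 1 gives a raised CO no force against a denial, and no other section gives the CO reading at Visits 2-6 a consequence. The smoking-abstinence statements in the synopsis, Section 9.1 and Section 10.6 contradict each other and must be reconciled.

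The only size that can be attached is for one undetected same-morning episode: 5.8 to 14.4 ng·h/mL added to that period's AUCinf, under the assumed residual and half-life. How often this would happen is unknown.

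Two stronger readings are tempting and not supported. One is to express the addition as a percentage bias in the product comparison. The protocol gives no expected AUCinf, so a percentage needs a further assumption, and it would describe one contaminated period, not a treatment contrast. The other is to attach the figure to the 8 pm versus 24 h conflict; at the same half-life about 1/64 remains after 12 h, so that conflict alone has little effect on AUCinf.

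No stated sample size, power or significance level changes. The case for acting is that the criterion defeats its own objective check and is cheap to correct.

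**What to change.** 1. Reword exclusion 1 so that either self-reported smoking within the abstinence window or CO above 10 ppm is sufficient.
2. State in Section 12.4.7 and Table 1 that the CO result is applied before dosing at each of Visits 2-6, and what follows for the session if it fails.
3. Reconcile the synopsis, Section 9.1 and Section 10.6, no. 2, into one smoking-abstinence window chosen by the sponsor, supply the missing unit, and say that this is the window the subject certifies.

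**Cost.** Edits to a few sentences and a table note; CO is already scheduled at these visits, so there is no new procedure. The price is an occasional screen failure or a missed or rescheduled session. A missed session could take a subject out of the per-protocol set, which requires completion of the study period (Section 17.3.2), so the protocol should say whether rescheduling is allowed. Withdrawn subjects are not replaced.

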10.6 Restrictions during the study

- 1. Subjects shall be abstinent from snus and all other nicotine containing products from 8.00 p.m. the night before each trial day.
- 2. Subjects shall abstain from smoking the last 24 before each study day.

- 3. The subjects are not allowed to eat or drink, or use any other mouth related procedure (e.g. tooth brushing) 30 minutes before dose administration, during application of investigational products and 30 minutes after the investigational product have been taken out. [5].
- 4. Other therapy considered necessary for the subject's welfare may be given at the discretion of the Investigator. All such therapy must be recorded in the Case Report Form.
- 5. The female volunteers are expected to be sexually abstinent or use contraceptives to prevent pregnancy during the study period
- 6. Consumption of grapefruit and/or grapefruit containing products is not allowed 1 week before IP dosing until last PK day.
- 7. Xanthine or taurine containing products/beverages, e.g. Redbull, are not allowed during the study.
- 8. Abstain from drugs of abuse from Screening to Follow-up visit.
- 9. The subjects must not donate blood or plasma during the study until three months after the Follow-up Visit.
- 10. Study subjects are not allowed to participate in any other clinical study during the study period.

10.7 Criteria for subject withdrawal

10.7.1 General withdrawal criteria

A subject should be withdrawn from the study treatment if, in the opinion of the Investigator, it is medically necessary, or if it is the wish of the subject. The reason for withdrawal should be clearly described and the subject should, whenever possible, irrespective of the reason for withdrawal, as soon as possible be medically examined. Relevant samples should be obtained and all relevant assessments should be completed, preferably according to the schedule for the final assessment. The Case Report Form should be completed as far as possible and collected by the staff.

10.7.2 Procedures for discontinuation of a subject from the study

A subject who prematurely discontinues participation in the study will be asked about the reason(s) for discontinuation and the presence of any AEs. If possible he/she will be seen by the Investigator and assessed according to the procedures scheduled for the follow-up visit. Any ongoing AEs will be followed as described in Section 12.6.6.

10.7.1 Subject replacement

Subjects who are prematurely withdrawn from the study for any reason will not be replaced.

10.8 Randomization

Subjects will be assigned to the treatments using a computer-generated randomization list.

10.9 Blinding

The present study will be an open randomized study. Subjects will be administered each dose by the personnel according to the randomization list.

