Subjective effects – Each subject's rating of product "strength" using a Visual Analogue Scale (VAS): (head "buzz", "head rush", "hit", feeling alert, overall "product strength"), anchored with "not at all" to "extremely". VAS scores will be obtained at the following time points before (0), 5, 10, 15, 30 and 60 minutes after each product is administered.

Safety assessments

Adverse Events will be collected starting with administration of the Investigational Product until the last follow-up from the first dose.

Statistical methods

The study will include 18 subjects. A previous study (Lunell E & Curvall M 2011) has made the calculation of sample size possible. Nicotine extraction from 1 g Swedish portion snus containing 8 mg nicotine/pouch was estimated at 2.18 ± 0.92 mg per 1 g portion. Under the assumption of a complete dissolution and extraction of the 3 and 6 mg ZYN® products, respectively, versus the 2.18 ± 0.92 mg nicotine, and a standard deviation of 5.0 the estimated sample size is 16 with a power of 80% and alpha=0.05.

3 TA	BLE OF CONTENTS	
2 STU	UDY SYNOPSIS	4
3 TA	BLE OF CONTENTS	7
4 LIS	T OF ABBREVIATIONS AND DEFINITIONS OF TERMS	11
5 IMI	PORTANT MEDICAL PROCEDURES TO BE FOLLOWED BY THE	
	INVESTIGATOR	
5.1	Medical emergencies contacts	13
	Overdose	
6 INV	/ESTIGATOR(S) AND STUDY ADMINISTRATIVE STRUCTURE	
6.1	.1 Investigational Product manufacturing and packaging	15
6.1		
7 INT	RODUCTION	16
7.1	Project background	16
7.2	Investigational products	17
7.2	2.1 Product characteristics	17
7.3	Risk/benefit assessment	17
7.3	S.1 Summary of risk management	17
8 STU	UDY OBJECTIVES AND ENDPOINTS	18
8.1	Primary objective(s)	18
8.1	.1 Primary endpoint (s)	18
8.2	Secondary objectives	18
8.2	2.1 Secondary endpoints	18
9 INV	/ESTIGATIONAL PLAN	19
9.1	Overall study design and schedule of events	19
9.2	Rationale for study design and dose groups	21
10 ST	CUDY POPULATION	21
10.1	Recruitment	21
10.2	Screening and enrolment log	21
10.3	Number of subjects	21
10.4	Inclusion criteria	21
10.5	Exclusion criteria	22
10.6	Restrictions during the study	22
10.7	Criteria for subject withdrawal	23
10.	7.1 General withdrawal criteria	23
10.	7.2 Procedures for discontinuation of a subject from the study	23
CONFI	DENTIAL 7 (45)	

10.7	.7.1 Subject replacement	23
10.8	Randomization	24
10.9	Blinding	24
11 TR	REATMENTS	24
11.1	Identity of investigational products	24
11.2	Packaging and labelling	24
11.3	Conditions for storage	24
11.4	Dispensing and accountability	24

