6.1.1 Investigational Product manufacturing and packaging

The investigational and reference products will be manufactured and packaged compliant with Swedish law on food production. The investigational and reference products will be transferred from the original container, weighed and individually packaged in identical sealed food approved test containers at Swedish Match analytical lab.

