6.1.2 Identity of investigational products

Each dose of the investigational and reference products will be delivered in separate identical food approved glass containers labeled with unique identification numbers.

Signatures required are provided in Appendix 18.1.

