11.2 Packaging and labelling

Investigational products will be delivered to the study site in identical containers labeled with unique identification numbers by Swedish Match in accordance with the randomization list.

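### Nothing in the open design keeps ZYN strength or process from the people rating and recording the VAS, although every dose already comes in an identical ID-coded container

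*Protocol*

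**What the plan says.** Section 10.9 of the protocol declares: "The present study will be an open randomized study". It continues: "Subjects will be administered each dose by the personnel according to the randomization list". The title page, synopsis and section 9.1 also call the design open. None of them gives a reason.

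The packaging sections describe coded single doses:

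- Section 6.1.1: test and reference products are "transferred from the original container, weighed and individually packaged in identical sealed food approved test containers" at the sponsor's analytical laboratory.
- Section 6.1.2: each dose comes in "separate identical food approved glass containers labeled with unique identification numbers".
- Section 11.2: delivery to the site is in "identical containers labeled with unique identification numbers by Swedish Match in accordance with the randomization list".

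Sections 8.2.1 and 12.5.2 make the VAS for head buzz and related items, including overall product strength, a secondary endpoint. It is self-rated on a 100-mm scale from predose to 60 minutes and described as a proxy for systemic uptake. Section 17.6 tests the within-subject differences with both a Wilcoxon signed rank test and a t-test. Section 17.1 sets two-sided 5%, and section 17.7.3 makes no multiplicity adjustment.

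Section 17.1 fixes the comparison of each ZYN article with snus and leaves comparisons among the ZYN articles to the SAP. Section 11.1 lists four ZYN Smooth articles: 3 mg and 6 mg, each from two manufacturing processes.

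**The concern.** A person who knows that a pouch is the 3 mg or the 6 mg version has been given part of the answer to a question about how strong it is. The person handing over the VAS ruler can also convey that knowledge. If this happens, a lower rating for a 3 mg pouch may reflect expectation as well as nicotine uptake, and the VAS becomes a weaker proxy for uptake.

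This can affect the ZYN-versus-snus contrasts that the protocol fixes, because the ZYN side of each contrast is rated with or without knowledge of its strength. It matters most for any comparison of 3 mg with 6 mg, or of one process with the other, should the SAP include one.

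Expectation enters when the rating is made, so no later analysis can remove it. It has to be dealt with in the protocol.

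**Working it through.** **Step 1. What the protocol lets people know.** Three facts side by side:

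- The study is open and staff dose from the randomization list (10.9).
- The container that reaches the site is identical for all products and is described as carrying an ID number (6.1.2, 11.2).
- No section says that strength or process is disclosed to the subject, and none says that it is withheld.

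The supportable statement is therefore that nothing prevents the knowledge. The documents do not show that the subject has it.

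**Step 2. Which endpoints are exposed.**

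- AUCinf (8.1.1) and the other plasma parameters come from an LC-MS/MS assay (12.5.1).
- Extracted nicotine comes from laboratory analysis of the pouches (13.2).
- Pulse rate is read by an automatic device (12.5.2).
- The VAS is the subject's own judgement and is the endpoint at risk.

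**Step 3. What an expectation shift would do to the test.** The protocol gives no SD for the VAS and no figure for an expectation effect, so there is no figure in the plan to reproduce. The inputs are:

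- n = 18 pairs (section 10.3) and two-sided alpha = 0.05 (section 17.1), with the paired t-test of section 17.6.
- Assumed: true difference 0; expectation shift b = 5 or 10 mm; SD of within-subject differences s = 15, 20, 25 or 30 mm.

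The noncentrality is δ = (b/s)·√18, with 17 degrees of freedom and critical value 2.110. The chance of p<0.05 is P(|T| > 2.110), where T is noncentral t with parameter δ. For example, b = 10 and s = 20 give δ = 0.5 × 4.243 = 2.121 and a probability of 0.52.

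| SD of differences (mm) | δ, 5 mm | p<0.05, 5 mm | δ, 10 mm | p<0.05, 10 mm |
|---|---|---|---|---|
| 15 | 1.414 | 27% | 2.828 | 76% |
| 20 | 1.061 | 17% | 2.121 | 52% |
| 25 | 0.849 | 13% | 1.697 | 36% |
| 30 | 0.707 | 10% | 1.414 | 27% |

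With no shift the rate is 5%. The 76% needs the larger shift and the smallest SD together. The table shows how sensitive the test would be to a shift; it is not evidence that a shift occurs.

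**The case against.** The case for leaving the design alone has real substance.

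- **Disclosure is not documented.** A reader might infer that subjects see a 3 mg or 6 mg label. The protocol does not say so: the containers are described with ID numbers, and the subject information is not available for review. This stands, and it limits the point to a risk that the plan leaves open.
- **There may be a practical reason.** A reader might infer that the open design serves no operational purpose. The protocol merely gives no reason. A coded container masks the package and not the pouch once it is taken out. No section says that the four ZYN articles look, taste or feel alike. Single coded containers also serve weighing, identification and accountability. This stands: masking within ZYN may be imperfect, and the containers need not have been meant for masking.
- **The fixed comparisons are against snus.** Daily snus users will recognise it, and the within-ZYN comparisons are left to the SAP. This stands in part. Product type cannot be hidden, but withholding ZYN strength still removes one source of expectation from the ZYN side of each contrast.
- **The VAS is secondary.** Section 7.1 describes it as a supplement to the extraction and plasma data. This stands, and it limits the severity. The VAS is nevertheless formally tested.

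**Conclusion.** The point holds as a limited one. The protocol declares an open study without a stated reason and leaves subjects and VAS staff free to know the ZYN strength and process, although coded single-dose packaging is already planned. That may bias the self-rated VAS endpoints. The primary endpoint and extracted nicotine are not materially affected.

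Neither the size nor the direction of any bias can be derived from the documents. Under the assumed shifts of 5 and 10 mm and SDs of 15 to 30 mm, p<0.05 would occur in about 10-27% and 27-76% of trials respectively, against a nominal 5%.

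The documents do not support the stronger reading that the VAS results are biased, or that subjects are told the strength. This is an inexpensive improvement, between worth considering and advisable, held with medium confidence.

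**What to change.** Amend section 10.9 along these lines:

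- The study is open for snus versus ZYN. ZYN strength and manufacturing process are withheld from subjects and from the staff who take the VAS until the data are locked.
- The site's randomization list shows container IDs only, and staff dispense by ID.
- The key from ID to product stays with the sponsor's existing packaging laboratory, with a code-break route for medical need.
- The subject information does not disclose strength or process by session.

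If the sponsor prefers to stay fully open, the protocol should give the reason, state what subjects and VAS staff know at each visit, and treat the VAS results as exploratory.

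**Cost.** No new containers, visits or staff are needed. The work is a protocol amendment, a revised site list, a check of the subject information and a code-break procedure. Under section 14.5 the amendment goes to the ethics committee for approval or notification. Masking will be partial, because snus is recognisable, ZYN pouches may differ in look or taste, and some subjects may guess the strength.
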